### 16.1 Interim Safety and Conduct Assessment

---

This feasibility study is the first to study patients undergoing PUL with AR. As such, the study progress will be assessed formally after the enrolment of the first 15 subjects. The TWOC success rate will be evaluated, as will the enrolment rate, screen failure reasons, related SAEs, and protocol compliance. In the event changes to protocol are warranted, enrolment may be paused until a protocol amendment or informed consent form is approved by HRA. If it is determined that the early success rate is unacceptable, the study may be terminated.

### 16.2 Per Protocol Population

---

The PP analysis population is a subset of the ITT population which excludes subjects who do not receive any implants or who have significant violations that impact the study data integrity.

### 16.3 Safety Population

---

The safety population will be used for all safety assessments. The safety population includes all enroled subjects with at least one UroLift device introduced. Safety assessments for enroled subjects whom later undergo surgical retreatment with any other surgical procedure will be censored on the day of the secondary intervention. Censoring in adverse event analysis will be applied only to alternative surgical retreatments and not to secondary PUL.

### 16.4 Missing Data

---

To protect the scientific integrity and validity of study, a robust data retention plan will be employed through 12 months and reasons for missing data or early exit will be collected. No imputation for missing data points is planned.

## 16.5 Analysis of Success Measures

---

### **Primary Study Assessment:**

TWOC is a binary measure of success. The percent of subjects who have a successful TWOC at the 3 day post procedure visit will be presented. Secondary assessments will include the catheter free rate at 1 month along with time without catheter. This primary study assessment will be calculated for both the ITT and the PP analysis populations.

## 16.6 Additional Assessments

---

Continuous measures will be summarised by visit. Summary statistics will include the available sample size, mean and standard deviation. Changes from baseline to each follow-up visit will also be calculated and the summary statistics will include the number of patients with change score available, mean, median, standard deviation, and confidence intervals (CI). These assessments will be calculated for both the ITT and PP analysis populations.

The Kaplan-Meier method will be used to calculate freedom from alternative secondary surgery over time and freedom from medical treatment, from the time of the PUL procedure for the ITT and PP populations. Subjects that do not have an alternative procedure will be censored at their last recorded follow-up visit. The probability of freedom from urinary retention will be analysed in a similar manner for the safety population. Time without catheter will be analysed using the Kaplan-Meier method in the ITT and PP populations.

Adverse events will be summarised by overall adverse events (AEs), severe AEs (grade 3 or higher on CTCAE scale), AEs related to device and/or procedure, serious adverse events (SAEs) and SAEs related to device and/or procedure. Adverse events will be coded using MedDRA and CTCAE v4.0 severity grades and will be presented by System Organ Class (SOC) and preferred term. Adverse events will be summarised for the safety population.

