## 1 Protocol Summary

Study Title	Prostatic Urethral Lift in Subjects with Acute Urinary Retention Study (PULSAR)
Study Objectives	Assess feasibility and safety of the Prostatic Urethra Lift (PUL) procedure in patients with acute urinary retention secondary to BPH. Research methodology will also be evaluated for larger, randomised study.
Study Design	Multi-centre, prospective evaluation of PUL and retrospective review of invasive surgery as potential comparator.
Sample Size	Up to 55 subjects treated with PUL. Retrospective chart review will include BPH patients that presented with AR and went on to de novo invasive surgery from June 1, 2015 to December 31, 2015.
Subject Population	Males over the age of 50 diagnosed with symptomatic benign prostatic hyperplasia (BPH) and ongoing acute urinary retention after failed TWOC.
Number of Centres (Sites)	Up to six centres in the United Kingdom.
Clinical Indication	The UroLift System is indicated for the treatment of symptoms due to urinary outflow obstruction secondary to benign prostatic hyperplasia (BPH) in men 50 years of age or older.
Primary Study Assessment	Successful post-procedure voiding trial without catheter (2-4 days).
Safety Assessment	Rate of serious adverse events (SAEs) related to BPH intervention through 3 months.
Additional Assessments	1. Need for further clean intermittent self-catheterisation (CISC) 2. Urinary symptoms, post void residual (PVR) and peak flow rate over follow-up 3. Subjects free from urinary retention through 1 month, 6 weeks, 3, 6 and 12 months 4. Subjects free from alternative surgical procedure for BPH through 12 months 5. Duration of catheter prior to treatment and in follow-up between prospective (PUL) and retrospective (TURP/HoLEP) 6. Rate of AEs in prospective PUL and retrospective TURP/HoLEP 7. Assess enrolment rate, willingness of patients to enrol, inclusion criteria, and appropriateness of endpoint
Follow-up Evaluations	Post-procedure, 6 weeks, 3 months, 6 months (remote), 12 months
Anticipated Study Duration	
First patient in (FPI)	15-April-2018
Last patient in (LPI)	31-December-2018
Endpoint analysis	28-February-2019
Study close	01-April-2020

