## 6.4 Other Assessments

---

Several other outcomes will be analyzed during the 12 month follow-up to understand post-TWOC durability:

- Catheter free rate and days free from catheter at 1 month and throughout follow-up
- Number of subjects who failed initial attempt but are able to void in subsequent TWOC
- Need for further clean intermittent self-catheterisation (CISC)
- Urinary symptoms peak flow rate, post void residual (PVR) volume
- Subjects free from alternative surgical procedure for BPH
- Duration of pre-index procedure catheter and its impact on durability
- Rate of adverse events
- The prospective arm will be compared to the available data collected in the retrospective surgical arm

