Medical History by medical database	
 
• Prostatitis requiring treatment (antibiotics) within the last year
 
• Known bladder stone within the prior 3 months or treatment within 12 months
 
• Previous BPH or pelvic surgical procedure
 
• Prostate or bladder cancer history
 
• Prostate biopsy (allowed if negative and <math>\geq 6</math> wks)
 
• Neurogenic or atonic bladder
 
• If available, pre-procedure IPSS, peak flow rate, and PVR within 6 months
 
	In screening up to index procedure; review of database should be completed as close to index procedure as possible.	
 
• These criteria should be confirmed through patient interview and consistent with medical chart. Diagnostic testing not required unless symptomatic.
 
• A thorough medical history should be documented to assist with adverse event reporting after enrolment, as each AE will require assessing if pre-existing or new.
 

Medical History by patient interview	
 
• Unable or unwilling to complete all required questionnaires and follow up assessments
 
• Desire to maintain fertility post procedure
 
• Currently enroled in any other clinical research study that has not completed primary endpoint
 
	Prior to procedure	
 
• Erectile health will be a part of the questionnaires and participants should be willing to complete.
 

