#### 10.4 Post-Procedure Trial Without Catheter (TWOC)

The subject will return to clinic **3 days ( $\pm 1$  day)** after Index procedure for the primary study assessment screening of bladder function without catheter. TWOC will be considered successful if the spontaneous void is  $\geq 100$  mL with PVR  $< 300$  mL. If subject fails the initial TWOC, at least one additional TWOC will be performed per standard of care. All catheterisations will be recorded on the eCRF.

The following evaluations will be performed in office **3 days ( $\pm 1$  day)** after index procedure in conjunction with the TWOC:

- Relevant Concomitant medications: BPH/LUTS; Sexual Function; GU; Prostate Cancer
- Freestanding uroflow and post void residual (PVR)
- Catheterisation review
- Adverse Event review; Intervention review

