#### 10.5 6 Week Follow-up Procedures

The following evaluations will be performed in office **6 Weeks ( $\pm 7$  days)** after index procedure:

- Questionnaires to be completed by the subject:

- Urinary Symptoms questionnaires including IPSS & QoL (International Prostate Symptoms Score with Quality of Life) and BPHII (Benign Prostatic Hyperplasia Impact Index) unless current indwelling catheter.
- SHIM (Sexual Health Inventory for Men): Recall period for this visit should cover only post-enrolment activity. Completed if subject was sexually active at baseline.
- Return to Normal
- Patient Satisfaction
- Symptom questionnaire upon occurrence (includes: Incontinence Severity Index (ISI), haematuria, dysuria, pelvic pain VAS)
- Relevant Concomitant medications: BPH/LUTS; Sexual Function; GU; Prostate Cancer
- Urinalysis (urine culture and sensitivity if abnormal, clinically significant and indicates a urinary infection). UA not required if current indwelling catheter.
- Freestanding uroflow and post void residual (PVR)
- Voiding Assessment
- Catheterisation Review
- Adverse Event Review; Intervention Review

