**Table 7 Schedule of Procedures**

Tests and Assessments	Screening	Index Procedure Through Release	Clinic Visit Post-procedure (3 days ± 1 day)	Clinic Visit 6 Weeks (± 7 days)	Clinic Visit 3 Months (± 14 days)	Phone Visit  6 Month (± 14 days)	Clinic Visit 12 Months (± 30 days)	Study Exit
Informed Consent must be documented prior to any procedures outside standard of care				Urinary Symptoms and UA are not required if subject is on current indwelling catheter.				
Subject Questionnaires								
Urinary Symptoms				X	X	X	X	
SHIM	If sexually active within the last 6			If sexually active at baseline	If sexually active at baseline		If sexually active at baseline	
Incontinence Severity Index				If reported	If reported	If reported	If reported	
Dysuria				If reported	If reported	If reported	If reported	
Haematuria				If reported	If reported	If reported	If reported	
Pelvic Pain VAS				If reported	If reported	If reported	If reported	
Return to Normal				X	X (if not previously achieved)			
Patient Satisfaction				X	X	X	X	
Subject Interview								
Medical History	X							
Concomitant Medications	X	X	X	X	X	X	X	
Voiding Assessment				X	X	X	X	
Intervention Review	X		X	X	X	X	X	
Testing								
Freestanding uroflow; PVR^3			X	X	X		X	
Urinalysis (UA)	X			X	X		X	
Urine Culture and Sensitivity	If indicated			If indicated	If indicated		If indicated	
Investigator Completed								
DRE	X				X		X	
Urodynamics	X 						X	
US	X 							
Cystoscopy (flexible)	X 						X	
Procedure		X						
Catheterisation Review	X	X	X	X	X	X	X	
Trial Without Catheter (TWOC)			X 					
Adverse Event Review		X	X	X	X	X	X	
Subject Discontinuation								X

 Office or phone visit acceptable. If subject returns to clinic due to an AE, any testing will be entered in EDC as interim (if outside visit window).

 Relevant medications and interventions only: BPH, LUTS; Sexual Function; GU; Prostate Cancer.

 Uroflow strip chart recordings, abnormal UA and urine culture results, urodynamics reports, and cystoscopy videos collected in the study will be retained as a part of the dataset and must be redacted.

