### PROTOCOL REVISION HISTORY

Protocol Revision	Revision Date	History
A	30 May 17	Initial Release
B	31 Jan 18	

1. Replaced unanticipated with unexpected adverse event throughout.

2. Clarified SAE reporting requirements

3. Replaced CEC with an Independent Safety reviewer.

4. Revised TWOC endpoint to 300 ml PVR.

5. Updated to note urodynamics testing may be performed at each study site if a testing facility is available and a qualified operator is on-site

6. Removed urodynamics and Active UTI from eligibility procedures

7. Clarified language surrounding procedure antibiotics

8. Clarified UA and urine culture requirements.

9. Removed Active Urinary Tract Infection and active gross hematuria from exclusion criteria

10. Removed reference to IPP size for inclusion for prospective arm

11. Revised exclusion criteria language for prospective arm: #5, #10 and #11

12. Revised inclusion criteria for retrospective arm: excl. #5 and #6

13. Revised exclusion criteria for retrospective arm: #3, #5 and added #8.

14. For retrospective arm, updated to include all site invasive BPH surgeries.

15. Removed reference to protocol deviation waivers & over-read for enrolment.

16. Removed refresher training

C	12 August 2018	

1. Removed symptom questionnaire requirements at screening.

Protocol Revision	Revision Date	History

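### By-visit means and changes for symptoms, peak flow and PVR are labelled ITT, but no baseline is scheduled and from 6 weeks they describe mainly unretreated men without an indwelling catheter

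*Combined protocol and SAP*

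**What the plan says.** The Protocol Summary lists "Urinary symptoms, post void residual (PVR) and peak flow rate over follow-up" among the additional assessments, and Section 6.4 lists "Urinary symptoms peak flow rate, post void residual (PVR) volume". Section 16.6 summarises continuous measures by visit and continues: "Changes from baseline to each follow-up visit will also be calculated". Both kinds of summary are assigned to the ITT and PP sets. Section 16 defines ITT as every enrolled man in whom at least one device was introduced.

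On baseline, Table 7 has no screening mark for urinary symptoms or for uroflow and PVR. Table 5 asks for a chart value: "If available, pre-procedure IPSS, peak flow rate, and PVR within 6 months". The revision history shows that the symptom gap was a deliberate change at revision C: "Removed symptom questionnaire requirements at screening". Section 10.14.1 explains the setting: men are on a catheter for retention when screened.

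On follow-up, Table 7 states: "Urinary Symptoms and UA are not required if subject is on current indwelling catheter". Sections 10.5 to 10.8 repeat the symptom waiver at each symptom visit, for example "Benign Prostatic Hyperplasia Impact Index) unless current indwelling catheter" at 6 weeks. Section 10.8 also waives uroflow and PVR at 12 months for an indwelling catheter or a preventing adverse event. Section 10.10.1 requires only the 12-month visit once alternative surgery is scheduled. Section 16 censors effectiveness data from the day after any surgical retreatment, including repeat PUL. Section 16.4 plans no imputation.

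**The concern.** Continued catheter dependence and prescribed surgery are among the outcomes that Section 10.11 uses to judge treatment failure. They are also what removes a man's symptom scores, and often his flow and PVR, from the visit summaries. Absence is therefore tied to poor outcome, while the label says that all enrolled men are described. The change scores need a starting value as well, and for these measures one exists only by chance of record-keeping.

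The study is meant to inform a larger one, and Section 6 says that no study has yet shown whether PUL works as well in retention as in voiding men. A planner could read an ITT symptom mean, or set it beside the ITT IPSS changes quoted in Section 5.1.1, as if it described everyone treated.

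**Working it through.** **1. What is available at each visit** (Table 5, Table 7, Sections 10.4 to 10.8 and 10.10.1)

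| Visit | Symptom scores | Uroflow and PVR |
|---|---|---|
| Screening | not scheduled; on-file IPSS if it exists | not scheduled; on-file values if they exist |
| Day 3 | not scheduled | scheduled for all |
| 6 weeks, 3 months | waived with indwelling catheter; not owed once surgery is listed | scheduled, no written catheter waiver; not owed once surgery is listed |
| 6 months | waived with indwelling catheter; not owed once surgery is listed | not scheduled |
| 12 months | waived with indwelling catheter | waived with indwelling catheter or preventing adverse event |

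Counts:
- Measures with a scheduled baseline: 0 of 5 (IPSS, QoL, BPHII, peak flow, PVR).
- Symptom visits with a catheter waiver: 4 of 4.
- Uroflow and PVR visits with an express catheter waiver: 1 of 4.
- Symptom visits that can lapse on surgical listing: up to 3 of 4.

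At 6 weeks and 3 months, a man with an indwelling catheter is unlikely to supply a freestanding flow. Section 10.14.6 admits only a PVR taken after a valid uroflow. That these men drop out of the flow and PVR means at those two visits is therefore an inference, not a written rule. Screening urodynamics does not supply the missing baseline, because it is optional by site.

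**2. Direction.** For visit means, the men removed are mainly those still catheterised, awaiting surgery or retreated, so the remaining mean probably looks better than the whole group would. For change scores there is a second influence. An on-file value up to 6 months old may pre-date the retention episode and so may understate how far a man has come from retention. Selection pushes the other way, and the net direction is unknown.

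**3. Size.** The plan has no figure to reproduce, and the documents give no rate of catheterisation, surgical listing or retreatment after PUL in retention. The bias in a mean cannot be computed. Two illustrations show what is at issue. The shares f, b and r are assumptions.

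*Numbers contributing.* With N = 55 (the maximum), let f be the share unassessed at a visit and b the share with an on-file baseline, independent of f. Then n for a mean = 55(1 − f), and n for a change = 55(1 − f)b.
- f = 20%: 44 men in the mean; 44 × 0.25 = 11 or 44 × 0.50 = 22 with a change score.
- f = 40%: 33 men in the mean; 33 × 0.25 ≈ 8 with a change score.

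*Observed-case against all-enrolled proportion.* If k of 55 men are absent and count as non-responders, and a proportion p of the assessed men respond, the all-enrolled figure is p(55 − k)/55. The gap is p·k/55, at most 1/55 = 1.8 percentage points per absent man. With r, the assumed share of assessed men responding, at about 80%:

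| f | Observed-case | All enrolled | Gap |
|---|---|---|---|
| 10% | 40/50 = 80% | 40/55 = 73% | 7 points |
| 20% | 35/44 = 80% | 35/55 = 64% | 16 points |
| 40% | 26/33 = 79% | 26/55 = 47% | 32 points (31.5 before rounding) |

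The gap applies to the proportion proposed in the fix and follows from counting absent men as non-responders. It does not measure bias in an IPSS, flow or PVR mean.

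**The case against.** The strongest reply is that the absent men are counted elsewhere. The Protocol Summary lists freedom from retention through 1 month, 6 weeks, 3, 6 and 12 months and freedom from alternative surgery. Section 6.4 adds the catheter-free rate throughout follow-up. Sections 16.5 and 16.6 analyse TWOC, catheter and surgery outcomes, and the retrospective comparison repeats recurrence and retreatment. Section 16.6 also reports the available n, and Section 16.4 collects reasons for missing data. All of this stands. A reader might infer that the plan hides its failures, and the documents do not support that. What is missing is any summary that puts symptom, flow or PVR status together with catheter and retreatment status from 6 weeks on. A reported n shows how many men are absent but does not change whom the mean describes.

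A reader might also infer that Section 16.6 contradicts itself by planning changes with no baseline. That goes too far. The sentence covers continuous measures in general. SHIM has a scheduled baseline in sexually active men, as does urodynamics where a site offers it. A voiding baseline is also largely unobtainable in catheterised men, so its absence follows from the population. The deletion in the revision history is not an error in itself; Table 7 shows the gap without it.

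Three other readings would be too broad. Day-3 uroflow and PVR are scheduled for everyone and largely unaffected. The waivers cover indwelling catheters only, so men on CISC still contribute. An on-file IPSS may carry its QoL item.

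**Conclusion.** The point holds for IPSS with QoL, BPHII, peak flow and PVR. From 6 weeks on, summaries labelled ITT will describe mainly unretreated men without an indwelling catheter, and change scores will rest on whatever chart values exist. The visit means probably favour the device. This assumes that some men remain catheterised, are listed for surgery or are retreated, and that they would have scored worse. The amount cannot be derived, and the direction for change scores is uncertain. It would be wrong to quote 1.8 points per man as the bias in these means.

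Severity is minor to moderate. These are descriptive secondary measures in a feasibility study with no formal success criteria. The primary assessment, safety analysis and sample size are untouched. A misleading label still matters, because the results are meant to guide a larger trial.

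**What to change.** 1. Label the visit means and changes for these measures as observed-case. Beside each, tabulate the men absent by reason (indwelling catheter, surgery listed, retreated, other), using the reasons that Section 16.4 already collects.
2. Add the proportion of all enrolled men who meet an absolute cut-off prespecified by the sponsor: for IPSS at 6 weeks, 3, 6 and 12 months, and for PVR or peak flow at 6 weeks, 3 and 12 months. Day 3 is left out because the primary TWOC assessment already covers it. An absolute value avoids failing men for lack of an on-file baseline. Count men with an indwelling catheter or prior retreatment as non-responders. State in advance how CISC users and men with implant removal only (Section 10.10.2) are classed. Show men missing for other reasons separately, with an observed-case sensitivity figure.
3. Present change from baseline for these measures as exploratory, only in men with an on-file value, giving n and the date of that value relative to the retention episode. Omit it where no baseline exists.

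The cost is SAP wording and one or two extra tables, with no new visits or data. Symptom results will look less favourable.

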**Table 2 Definitions**

Adverse event (AE)	An adverse event (AE) is defined as any undesirable medical occurrence in a clinical trial subject, whether it is considered to be related to the device or not, that includes a clinical sign, symptom, or condition.  Once a subject is enroled, all AEs must be reported through follow-up period. Only exacerbated conditions or new onset qualify as an AE. Principal Investigator will assess severity, relatedness, serious or unexpected.
Alternative Surgical Intervention	A post-index procedure surgery, other than PUL, to treat BPH.
Acute Urinary Retention	Painful inability to void and a residual volume < 1500 mL.
Invasive BPH surgery	
 
• Transurethral resection of the prostate (TURP)
 
• Transurethral Laser (PVP, HoLEP or Interstitial)
 
• Open Prostatectomy
 

Index procedure	The first procedure to which subjects are enroled.
Precipitated AR	Acute urinary retention that develops in response to a trigger such as UTI, anaesthesia, surgery, medications with sympathomimetic or anticholinergic effects.
Serious Adverse Event (SAE)	
Serious Adverse Event (SAE) is defined as untoward occurrence that: (a) results in death; (b) is life-threatening; (c) requires hospitalisation or prolongation of existing hospitalisation (d) results in persistent or significant disability or incapacity; (e) consists of a congenital anomaly or birth defect; or (f) is otherwise considered medically significant by the investigator.
 
(in-patient hospitalisation is at least 24 consecutive hours)

Unexpected Adverse Event	An unexpected adverse event is an event which by nature, incidence, severity or outcome has not been identified in the current version of the Sponsor risk management files.
Spontaneous AR	Associated with older age, BPH, elevated PSA, or presence of severe LUTS.
PUL Procedure Time	Time from first device insertion to last device removed.

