Men failing a single TWOC have limited options to restore voiding. Long-term catheter management may be elected, either indwelling or intermittent clean catheterisation (CISC), which carries a burden of maintenance and frequent UTIs (over half will experience). Catheter use carries with it risk of haematuria, and less common AEs such as urethral diverticula and ischemic necrosis of the penis. Many patients will opt instead to undergo an invasive BPH surgery such as TURP, PVP or HoLEP. These surgical options are known to be effective in treating BPH, however, the safety and recovery profile are more severe than a minimally invasive procedure including possible permanent sequelae. The complication rates vary depending on procedure, but common to all include infection, bleeding, pain, stress incontinence, sexual dysfunction, incontinence, delayed recovery up to 3-6 months and re-treatment. The other reality of invasive surgery in U.K. is the long waiting period to secure OR time that extends time on catheter significantly. The waiting period averages 30 weeks to procedure after counselling the patient.

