#### 10.11 Treatment Failure

The early TWOC primary assessment is the standard data point to demonstrate urinary retention relief, however, does not consider long term durability. An independent urologist will review the outcomes of each subject and adjudicate if considered a treatment failure. The following outcomes will be reviewed to determine if a treatment failure:

- (1) The number of successful and/ or failed TWOCs.
- (2) Duration of dependence on indwelling catheter.
- (3) Prescribed surgical intervention.

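### Does the curve for freedom from alternative surgery mislead on durability because men still waiting for an operation are censored as event-free?

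*Combined protocol and SAP*

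**What the plan says.** Table 2 defines an alternative surgical intervention as "A post-index procedure surgery, other than PUL, to treat BPH", so the event is an operation, not a decision or a listing. Section 16.6 plans a Kaplan-Meier analysis of freedom from it, timed from the PUL procedure, in the ITT and PP populations, with the rule "Subjects that do not have an alternative procedure will be censored at their last recorded follow-up visit". Section 1 sets the horizon at 12 months.

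Section 6.4 introduces the list that holds this outcome with "Several other outcomes will be analyzed during the 12 month follow-up to understand post-TWOC durability". The same list has catheter-free rate and catheter-free days, success at a later TWOC, need for self-catheterisation, symptoms, flow and residual volume.

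Section 10.11 says of the primary assessment: "The early TWOC primary assessment is the standard data point to demonstrate urinary retention relief, however, does not consider long term durability". It continues: "An independent urologist will review the outcomes of each subject and adjudicate if considered a treatment failure". The inputs are the TWOC record, time dependent on an indwelling catheter, and "Prescribed surgical intervention".

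Sections 10.8 and 10.10.1 expect some men to be scheduled but not yet operated on. Scheduling waives the interim visits but keeps the 12-month visit. Section 16 mentions neither these men nor the adjudication.

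**The concern.** Section 6 says of invasive surgery in the UK: "The waiting period averages 30 weeks to procedure after counselling the patient". If men who fail PUL wait about as long, a decision made in the second half of the year leads to an operation after the last visit. Such a man is censored event-free and looks the same on this curve as a man who needs nothing more. Read as durability, the curve would then tend to flatter PUL and would depend partly on the length of the waiting list.

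The protocol has a measure that avoids this, since the adjudicator sees prescribed as well as performed surgery, but the analysis section gives it no table. The study is meant to help choose the endpoint for a larger trial (Sections 1 and 6.1), so a reader might carry forward an endpoint without knowing how many men were still waiting.

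**Working it through.** The plan gives no figure for this outcome, so there is none to reproduce. The check has three parts.

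**1. Timing.** Inputs: a mean wait of 30 weeks (Section 6) and a final visit at 12 months ± 30 days (Section 10.8). Applying that wait after PUL is an assumption; the documents give no post-PUL wait.

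- Wait in days: 30 × 7 = 210.
- Latest decision day with the operation done by day 365: 365 − 210 = 155, about week 22.
- For a visit at day 335: 335 − 210 = 125. For a visit at day 395: 395 − 210 = 185.
- Decision at 6 weeks: 42 + 210 = day 252, counted. At 3 months: 91 + 210 = day 301, counted. At 6 months: 183 + 210 = day 393, missed at day 365.

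Even with the full 30-week average, decisions that follow an early failed TWOC are counted. Only later decisions are lost.

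**2. Size.** Inputs: N = 55 (Sections 1 and 7) and complete follow-up (assumed). The estimate at 12 months is then 1 − operations/55.

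- Per pending man: 1/55 = 1.8 points.
- 95% half-width at 80%: 1.96 × √(0.8 × 0.2/55) = 0.106, or 10.6 points. In men, 0.106 × 55 = 5.8.
- Assume 11 men (20%) have surgery decided within the year. With none pending the curve reads 1 − 11/55 = 80.0%. With 1 pending, 1 − 10/55 = 81.8%. With 3 pending, 1 − 8/55 = 85.5%. With 6 pending, 1 − 5/55 = 90.9%.

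The share pending depends wholly on when decisions fall:

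| Assumed decision times | Wait | Share pending at day 365 | Gap if 20% decided |
|---|---|---|---|
| Even over the year | 30 weeks | 210/365 = 57.5% | 20 × 0.575 = 11.5 points |
| Front-loaded, scale 120 days | 30 weeks | 23.8% | 4.8 points |
| Front-loaded, scale 60 days | 30 weeks | 7.3% | 1.5 points |
| Even over the year | 6 weeks | 42/365 = 11.5% | 2.3 points |

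The front-loaded rows use an exponential truncated at day 365: share = 1 − [1 − exp(−155/s)]/[1 − exp(−365/s)], with s = 120 or 60.

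The decision rate, its timing and the wait all come from outside the documents, so the table shows sensitivity to assumptions and estimates nothing. The front-loaded gaps lie well inside the sampling error. The even spread fits poorly in a population whose failure can show at the day-3 TWOC.

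**3. Coverage elsewhere in the plan.**

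- Man waiting because of recurrent retention: an event in the Section 16.6 retention curve. He also appears in the time-without-catheter analysis and in the planned retention and catheterisation comparisons with the retrospective arm.
- Man waiting because of other urinary symptoms, allowed for in Section 10.10.1: not necessarily in those analyses. He would be known from the scheduling that triggers the visit waiver and from the adjudicator's review.
- Man scheduled who later voids: Section 10.4 says "If subject fails the initial TWOC, at least one additional TWOC will be performed per standard of care". For some such men event-free status may be right.

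The uncovered remainder is the second group and the surgical decision as such.

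**The case for a change.** The strongest case for a change is that the adjudication exists because the primary assessment does not address durability, yet it has no planned output. That omission needs no assumption about waiting lists. Adverse event tables will not fill the gap, because Section 14.3 excludes recurrent retention and the need for another procedure from adverse events. A scheduled man who also misses the 12-month visit is censored earlier, at a time when his risk of surgery is high. Reporting a count and a table would cost almost nothing.

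The omission is real, as a minor reporting gap. Each subject is to be adjudicated, and scheduled men are identifiable at sites because the visit waiver depends on it, so an analyst writing the final report would be expected to tabulate both. The early-censoring point is limited: the 12-month visit stays mandatory after scheduling, and Section 9 asks for retreatment status at withdrawal.

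A further curve counting the decision for surgery as the event has a weaker case. The documents define no decision date, and Section 10.10 lists only the date of the procedure. Recruitment draws partly on surgery waiting lists (Section 10.1), so listings made before PUL would have to be separated out. The event would rest on open-label judgement and would count men who later recover. Nor would the two curves bracket durability: Section 6 notes that men may choose long-term catheterisation, and those men are event-free on both.

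**Conclusion.** No change to the plan is needed. The event, the censoring rule and the 12-month horizon agree with each other, and the estimate is valid for operations performed. Over-reading that one curve as durability is possible, but Section 6.4 sets it among several outcomes, and the retention and catheter analyses show the men most likely to be waiting.

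What remains is added reporting that analysts can supply from information the protocol already has sites and the adjudicator handle. Its size is 1.8 points per man with surgery pending, given 55 men and complete follow-up; any total rests on decision rates, timing and post-PUL waits that the documents do not give. Section 16.7 sets no success criterion, and neither the TWOC result nor the 3-month safety rate is touched.
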